1.2 Research Question

1.2.1 Does the use of CPAP treatment for SDB in pregnant women with preeclampsia risk result in better blood pressure control and thus reduce related maternal and fetal complications than standard usual antenatal care in control group

1.2.2 We want to investigate whether our proposed screening algorithm for SDB specific to pregnancy is accurate and feasible in monitoring and diagnosis of SDB during pregnancy.

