3.7.2 Control Group

- Subjects will receive standard antenatal care and follow-up plan similar to the intervention group.

Primary outcome

- Systolic and diastolic blood pressure, which will be measured at rest using sphygmomanometer twice on both arms by research nurses during daytime ANC at 10:00-12:00 pm at randomization (GA 0-16 week), 1.5-2 month after randomization (GA 18-20 week), and 3-4 month after randomization (GA 24-28 week), 5-6 month after randomization (GA 32-34 week) and monthly (GA>35 week) until delivery

Secondary outcome

- 24-hour ambulatory blood pressure monitoring (daytime versus night time) using the non-invasive technique from pulse transit time (SomnoTouch NIBP).
- Pregnancy complication listed as composite endpoints below

(Composite endpoint): A combination of clinical endpoints in maternal and fetal outcomes, data from Ramathibodi hospital during 2013-2014) *

- **Composite 1:** hypertensive disorder of pregnancy;
- **Composite 2:** hypertensive disorder of pregnancy or preterm labor or fetal growth restriction
- **Composite 3:** Preterm labor or fetal growth restriction, or severe pre-eclampsia or eclampsia or death; (composite 3 incidence=10%)

*Given that the incidence of hypertensive disorder incidence= $136/3787=3.6\%$;
gestational diabetes incidence= $601/3787=15.9\%$; fetal growth restriction incidence= $157/3787=4.1\%$; preterm labor incidence=10%; and severe pre-eclampsia/eclampsia/HELLP syndrome incidence= $(43+ 1+3=46/3787=1.2\%)$, respectively.

- Individual component of the composite endpoints including incidence of hypertensive disorder of pregnancy, gestational diabetes, preterm labor, and fetal growth restriction
- Glucose level, Oral Glucose Tolerance Test (OGTT), HbA1C
- Fetal ultrasound results: uterine Doppler arterial blood flow, fetal growth restriction
- Neonatal outcome: birth-weight, APGAR score, Length of stay, NICU admission

- Placenta character: weight will be measured at birth by the neonatal nurse.

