3.10.4 Statistical analysis

- Baseline demographic and clinical variables will be summarized using mean and its standard deviation (SD) or median and inter-quartile range as appropriate for continuous data, whereas categorical variables are summarized in frequencies and percentage. Comparisons of baseline characteristics between the 2 groups will be performed using t-test for the continuous variables and χ^2 test for the categorical variables.

- A blinded evaluation is planned to assess the observed primary end point by a clinical outcome assessment committee.
- The null hypothesis of the primary outcome for the Δ change of blood pressure (DBP) between treatment and controls are tested at 2-sided significant level of p -value <0.05 using t -test.
- Analyses for repeated measurement of secondary outcomes for continuous variables such as 24-hour blood monitoring, glucose level, Uterine artery Doppler ultrasound pulsatile index, estimated fetal growth, at 6-8 weeks after randomization, and during 2-3rd trimesters compared to baseline are performed using a longitudinal data analyses with linear mixed model.
- Analyses of secondary outcome of categorical data such as composite outcome 1 to 3, and individual outcome, control of BP, or non-dipping BP pattern will be compared between CPAP and control groups using χ^2 test, or Fisher exact test as appropriate.
- Gestational diabetes, as one of the inclusion criteria, was not included in endpoint analyses as initially planned.
- Predictors for composite outcome, and individual outcomes will be analyzed with multivariate logistic regression model adjusting for other co-variates.
- Statistical analyses will be performed according to the intention-to-treat analysis. Per-protocol analysis will then be analyzed for the comparisons of the results.

- In addition, per-protocol (PPA) and as-treated analyses (ATA) with counterfactual approach were also applied to deal with protocol violation using instrumental variable regression.
- We did not apply imputation for missing data because they were not used for the analysis.
- All statistical analyses are considered significant at the threshold level of 2-sided p-value < 0.05. Statistical analyses are performed using STATA Version 13.1 (StataCorp, College Station, TX).
- Interim analysis was not performed as initially planned, due to lower than expected number of deliveries when 50% of enrollments were achieved. Decisions were reported to the Ethic committee for approval.

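### Three overlapping composites and their components are each judged at two-sided 0.05 with no multiplicity control, so the chance of a false-positive complications result is two to nearly four times that of a single test

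*Protocol*

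**What the plan says.** The primary test in Protocol section 3.10.4 is a t-test on the change in diastolic pressure: "The null hypothesis of the primary outcome for the Δ change of blood pressure (DBP) between treatment and controls are tested". The same section then sends a group of categorical secondary outcomes to chi-square or Fisher tests, "such as composite outcome 1 to 3, and individual outcome, control of BP, or non-dipping BP pattern", and a group of repeated continuous ones to mixed models, including "24-hour blood monitoring, glucose level, Uterine artery Doppler ultrasound pulsatile index, estimated fetal growth". One sentence governs them all: "All statistical analyses are considered significant at the threshold level of 2-sided p-value < 0.05".

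The secondary outcome list under section 3.7.2 defines the family for complications:

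- Composite 1 is hypertensive disorder of pregnancy alone.
- Composite 2 is "hypertensive disorder of pregnancy or preterm labor or fetal growth restriction".
- Composite 3 is "Preterm labor or fetal growth restriction, or severe pre-eclampsia or eclampsia or death".
- The components are listed again: "Individual component of the composite endpoints including incidence of hypertensive disorder of pregnancy, gestational diabetes, preterm labor, and fetal growth restriction".

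Complications are part of the research question in section 1.2, which asks whether CPAP will "result in better blood pressure control and thus reduce related maternal and fetal complications". Section 3.9.2 sizes each composite separately at a type I error of 0.05. It accepts Composites 1 and 2 and rejects Composite 3, which needs 492 per arm against 153 available.

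The only allocation of alpha in either document is for interim looks: 0.0052 and 0.048 for efficacy, and 0.016 for the Pocock safety looks in the Combined protocol and SAP. That does not deal with multiple endpoints.

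**The concern.** Significance on any one of these outcomes could be read as an answer to the complications half of the research question, and nothing in the plan says which outcome carries that answer. The outcomes are also partly the same outcome. Composite 1 repeats an individual component and lies wholly inside Composite 2. Composite 3 shares preterm labor and growth restriction with Composite 2.

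The family is not fixed either:

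- Composite 3 is ruled out in 3.9.2 but tested in 3.10.4.
- Gestational diabetes is a listed component in 3.7.2 but dropped from endpoint analysis in 3.10.4.
- Composite 2 includes emergency cesarean section in 3.9.2 but not in 3.7.2.

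At stake is the reading of an isolated p-value below 0.05 on one composite or component, which would look stronger than it is.

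**Working it through.** **The plan's own figure.** The documents state no error rate across endpoints. The related figure that can be checked is the primary sample size in 3.9.1 (DBP difference 2.5 mmHg, SD 7.4, two-sided 0.05, power 0.80):

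n per arm = 2 × (1.96 + 0.84)² × 7.4² / 2.5² ≈ 138, against 139 stated. Power at 139 per arm is 0.804. This reproduces, and it shows that the 0.05 was sized for one test.

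**Number of tests.** Three composites plus hypertensive disorder, preterm labor and growth restriction make six listed tests. They are five distinct tests, because Composite 1 is hypertensive disorder. Gestational diabetes is left out, following 3.10.4.

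**Reference under independence (an upper guide, since the outcomes overlap).**

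- Three tests: 1 − 0.95³ = 14.3%
- Five tests: 1 − 0.95⁵ = 22.6%
- In favour of CPAP only: 1 − 0.975³ = 7.3% and 1 − 0.975⁵ = 11.9%

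**Simulation with the overlap built in.** 20,000 trials with no effect, 167 per arm (3.9.1), composites formed from the 3.7.2 definitions, and chi-square tests (Fisher when an expected count is below 5). Inputs:

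- Lowest rates, from 3.7.2: hypertensive disorder 3.6%, growth restriction 4.1%, preterm labor 10%. These are hospital figures for 2013-2014.
- Highest rates, assumed because the documents give none for the trial's high-risk women: 30%, 10% and 15%.
- Severe pre-eclampsia at one third of hypertensive disorder, in line with 1.2% / 3.6% in 3.7.2.
- Correlation between components 0 or 0.3 (assumed).

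| At least one p < 0.05, no true effect | Either direction | Favouring CPAP |
|---|---|---|
| One test (nominal) | 5% | 2.5% |
| Three composites | 10.4-11.7% | 5.1-5.8% |
| Composites plus preterm labor and growth restriction | 16.1-18.9% | 8.2-9.5% |

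Monte Carlo error is about 0.2 percentage points. Running 180 per arm, for the later target of 360, gives 11.0% and 17.6% in either direction, inside these ranges. A separate run at 139 per arm with assumed rates of 20%, 12%, 10% and 6% (hypertensive disorder, preterm labor, growth restriction, severe pre-eclampsia) gave 11.3% and 17.6%.

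**Why the figures fall below independence.** The between-arm differences are correlated: 0.44-0.78 for Composites 1 and 2, 0.72-0.94 for Composites 2 and 3, and 0.16-0.38 for Composites 1 and 3. Overlap reduces the inflation but does not remove it.

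**The case against.** The best reply is that these outcomes are openly secondary. DBP has its own test and its own sample size, Composite 3 is flagged as unsupported by the sample size, and the research question ties fewer complications to better blood pressure with the word thus. No section says that any single significant composite establishes benefit. All of that is correct, and it is why the point concerns labelling and interpretation and leaves the primary conclusion alone. It does not settle the matter: the 0.05 rule expressly covers all analyses, the composites are individually sized at that level, and the link in the research question is not a formal gate.

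Three stronger readings are tempting but unsupported:

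- A reader might infer that the composites alone give a false claim of benefit well over 5% of the time. The 10-12% counts both directions; the part favouring CPAP is 5-6%. That is about twice the nominal 2.5%, but only slightly above 5%.
- A reader might count 15 to 20 secondary outcomes and infer a chance of 54-64% (1 − 0.95¹⁵ = 0.54; 1 − 0.95²⁰ = 0.64). That assumes independence and includes ambulatory pressure, glucose, Doppler and placental weight, which belong to none of the complication composites. With ten further outcomes added to the simulation, the figures are 40-52% in either direction and 22-30% favouring CPAP, and they describe a broader question than complications.
- A reader might infer that a null primary result would be presented as success through a composite. The documents neither say nor imply this.

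There is also a fair objection to making Composite 1 the gated key secondary outcome. Section 2.1 counts chronic hypertension among the hypertensive disorders of pregnancy, and 3.2.1 makes chronic hypertension a qualifying condition, so as worded some women meet that endpoint at entry. The single composite in the secondary objective (1.3.2) is closer to Composite 2. The choice belongs to the sponsor.

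**Conclusion.** The concern holds for claims about complications. With no true effect, the plan's rule gives about a 10-12% chance of at least one significant composite, and 16-19% with preterm labor and growth restriction counted. In favour of CPAP these are about 5-6% and 8-10%, against 2.5% for one test. The result is stable across the assumed rates and correlations, including the documents' own rates. Per-protocol, as-treated and logistic analyses at the same threshold were not counted and would raise the figures. The DBP test, taken as the primary as in 3.9.1 and 3.10.4, keeps its error rate. This should be corrected, but it does not threaten the main result.

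**What to change.** In 3.10.4, limit the 0.05 significance rule to the primary DBP test. State that all composites, components and other secondary outcomes will be reported as effect estimates with 95% confidence intervals, labelled unadjusted and supportive, with no significance claim. Align 3.7.2, 3.9.2 and 3.10.4 on the contents of Composite 2, the status of Composite 3 and the place of gestational diabetes.

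If one confirmatory complications claim is wanted, name a single composite before unblinded results are seen, test it only after DBP is significant, and define it so that women with chronic hypertension at entry do not already meet it. One pre-named test holds the false-positive chance at no more than 5% two-sided, or 2.5% in favour of CPAP. Parts of 3.10.4 are written in the past tense, so analysis may already be under way. If results have been seen, naming a composite now would be post hoc and only the reporting change remains open.

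The cost is one paragraph and no data. The downside is that no formal significance claim on complications can be made unless such a composite is pre-named, nor, under the gate, if the DBP test fails.

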3.10.5 Termination of subjects

Termination of each subject to continue in the allocated arm will be evoked if one of the below criteria are met:

- Subject's unwillingness during anytime of the study
- Life-threatening condition to the mother such as placenta previa, abruption placenta, severe preeclampsia, eclampsia, HELLP syndrome
- Progression of OSA to severe RDI>30
- Threatening condition to fetus
- Obstetricians concerns

3.10.6 Data Safety Monitoring Board (DSMB)

The concept of clinical equipoise is concerned and adopted in this trial. It is essential and ethical to randomize while uncertainty remains in the community about the merits of the treatment. For the protection of the trial patients, and the future patients whose treatment may be influenced by current trial, data monitoring will be therefore set up [54]. The data safety monitoring committee will take responsibilities as follows:

- Review a protocol and monitor if the protocol is violated
- Recruitment or accrual rate
- Data monitoring and completeness of data
 - Missing data
 - Loss follow up
 - Adverse events
 - Severe rhinitis requiring rescue medication
 - Epistaxis requiring ENT consultation
 - Pneumothorax
 - Excessive air in stomach requiring medication

[figure not shown]
Interim analysis will be performed 1 time, i.e., when recruitment rate reaches to 50% of total sample size (i.e., ~150) and at the end of the study. Study will be terminated using following stopping rule [54-56]:

- Overall complication (i.e., pneumothorax, severe epistaxis, death, etc.) \geq 10% in any intervention arm or exceeding the significant level in Pocock interim analysis

- Recruitment rate is 50% lower than as planning during 2 years
- Loss follow-up rate is as high as 30%
- Significant intervention effects using Obrien-Fleming stopping rule as below [51-53]:

No. of look	Interim	Level of significance O'Brien-Fleming α_T [111]
1	Interim 1	0.0052
2	Final	0.048

Work flow for DSMB

The DSMB will consist of the independent experts not involved in the study enrollment from the essential disciplines including obstetrician, sleep specialist, epidemiologist, and statistician.

Pre-planned interim analysis is intended to monitor the progress and the indications for premature termination of trial [54].

3.10.7 Adverse events

Although, CPAP has been used to treat SDB in pregnancy without any reports of serious side effects, serious and unanticipated adverse events may be anticipated in this population. Data on the following potential adverse events that may be related to the study maneuver will be recorded and evaluated as part of continuous safety monitoring during the trial.

- Severe rhinitis requiring rescue medication
- Epistaxis requiring ENT consultation
- Pneumothorax
- Excessive air in stomach requiring rescue medication

These outcomes will be evaluated on a monthly basis by PI, and if the incidence of any of these outcomes are determined to be 10% greater in any arm of the study, this information will be provided to the PI and committee and the data safety monitoring board (DSMB) for immediate consideration, and evaluated for consideration of termination of the study or treatment arm.

3.10.8 Protocol Violation

Protocol violation includes

- Patients who have been allocated to receive CPAP, but they are later failed to use CPAP following the protocol for any reason.
- Patients who have been allocated to receive a routine ANC but with medical reasons to make them receive CPAP or other intervention/s act like CPAP

- Co-intervention with other intervention such in forms of medication such as anti-hypertensive drug, aspirin, calcium supplement, or other intervention either by physician prescription or non-prescription during the study which might interfere with the result of the study.

Measures to prevent and monitor protocol violation includes

- Close follow up and monitoring of CPAP adherence and early troubleshooting by sleep specialist and sleep technician by means of clinic follow ups, telephone call, and information pamphlet in the CPAP group.
- Close follow up of controls in terms of education regarding general sleep hygiene during ANC follow ups with sleep specialist and information pamphlet.
- Records of medication taken by the subjects will be kept and reviewed for every ANC visit. Education to avoid non-prescription medication during pregnancy will be given.

Protocol violation will be reviewed by the principle investigator who will discuss with the involved staff and provide a written summary including steps taken to avoid future violations.

3.11 Ethical considerations

3.11.1 Informed consent

Pregnant women and/or spouse will be approached during antenatal care for informed consent by researcher or research assistant. Decision to participate or not to participate will not have effect on the subject's right to standard usual care. In the situation that subject refuses to participate in the study, researcher/co-investigator will ask for the permission to use their demographic data to be included in the analysis if they agree.

3.11.2 The ethics committee approval at all affected sites will be obtained prior to initiation of the study at that site

[figure not shown]
- The conduct of this research will be performed according to declaration of Helsinki.
- Informed consent must be signed from all subjects in order to participate in the study.
Subjects have the right to withdraw from the study at any time, even if she had agreed to participate earlier without interruption of the usual standard care.
- Subject confidentiality will be kept by using non-identifiable subject ID for data collection and analysis.
- In case of any adverse effect occurred during the study that is related to receiving or not receiving intervention, standard care of high-risk pregnancy will be provided to participants.
- Follow-up visits will be according to the usual care for high-risk pregnancy to limit the burden of transportation of the participant.
- Subjects will be provided with incentives for the coverage of transportation for follow up visit.
- Subjects will have the beneficiary of receiving screening for SDB in addition to standard care of high risk pregnancy.
- Ambulatory sleep testing will be performed by certified sleep technician supervised by sleep specialist. Sleep test will be done only when participant is in stable condition to safeguard safety of the subject.
- Discomfort of using CPAP machine will be taken care of by sleep technician and/or sleep specialist by providing troubleshooting as standard care of CPAP usage.

- There will be additional blood sample taken from the subjects not more than 10 ml besides the normal usual care.

[figure not shown]

## 1.1 Background and rationale

### **1.1.1 Magnitude of problem:**

Obstructive sleep apnea (OSA) is caused by the cyclical upper airway collapses during sleep resulting in arousals, sleep fragmentation, intermittent oxygen desaturation, and sympathetic activation [1]. The prevalence of OSA in general population varied from approximately 2% to 26% worldwide [2, 3]. Prevalence of OSA in general population approximates 4% in men, and 2% in women [2]. Similarly, the prevalence of OSA in Thai population approximates 4.3-4.4% (5.3-15% male; 1.9-3.9% female) [4, 5]. However, it has been estimated that up to 93% of women and 82% of men with moderate to severe OSA have still remained undiagnosed [6]. The prevalence of sleep disordered breathing (SDB) in high-risk pregnancy was also high, which ranged from 20% to 35% (16-21) as for diagnosis based on objective sleep tests (e.g., polysomnography (PSG) or Watch-PAT) [7-12]. Recent meta-analysis showed the pooled prevalence of SDB during pregnancy of 26.7% (95%CI: 16.9%, 34.4%,  $I^2=83.15\%$ ) [13]. However, prevalence of SDB in pregnancy remains uncertain depending on various factors such as population studied (high vs low risk), type of diagnostic measures, and trimester of study.

### **1.1.2 Disease burden and impacts**

Growing evidences indicated that sleep disordered breathing during pregnancy is associated with poor maternal and fetal outcomes, e.g., gestational hypertension (GHT), pre-eclampsia, gestational diabetes (GDM) and low infant birth weight as for evidences from meta-analyses [14-16]. This might be due to physiologic and hormonal changes in pregnancy and thus predispose towards development of new-onset or exacerbation of SDB [17].

However, diagnosis and screening of SDB during pregnancy are challenging. Although in-laboratory PSG is the gold standard diagnostic test, long waiting periods for appointments, particularly considering the short time-window to perform the test early during the pregnancy, and the discomfort induced by the sleep test may lead to absence of investigation [18, 19].

Thus, simple and accurate screening strategies should be investigated. Risk stratification for the probability of OSA in pregnant women will also help in prioritizing the need for further diagnostic sleep testing given the limited resources in many places throughout the world. Early diagnosis and treatment of OSA in pregnancy should be implemented given the potential benefit on pregnancy outcomes [20, 21].

Our recent systematic review and meta-analysis showed that conventional OSA screening questionnaire such as the Berlin questionnaire and Epworth sleepiness scale had poor performance during pregnancy. We conclude that the poor discriminative values might be related to the facts that 1) both OSA and pregnancy lead to similar sleep complaints; 2) that there is a continuous change in symptomatology and the severity of the sleep-disordered-breathing with progression of pregnancy; 3) that the standard and threshold to diagnose SDB during pregnancy has not been defined; 4) finally that the timing of the questionnaire administration is not standardized.

And there is a need for screening tool that take into account the change overtime of the symptoms of OSA, and pregnancy. New screening tools and strategies specific to pregnancy that enable us to sequentially screen and monitor for OSA throughout pregnancy should be developed.

